Furthering our understanding of the psychosocial sequelae of IBD in children and young adults is particularly important in light of evidence suggesting that symptoms of anxiety and depression may decrease adherence to treatment, thus impacting on longer term disease outcomes,(6) and has been emphasized in a recent call to action issued within gastroenterology to improve understanding and early identification of comorbidities associated with IBD.(10)

To the best of our knowledge, there have not been any large population-based studies assessing the association between psychosocial comorbidities in IBD in

children and young adults and disease related outcomes. The aim of this study is therefore to fill this data gap, and to examine the following objectives.

Such new insights will be valuable for clinicians in optimising patient care for IBD patients; allowing early interventions to be targeted to those most at risk, and potentially preventing the development of more serious mental health problems such as depression; linked to difficulties with medication adherence, and anxiety; which may exacerbate future disease activity.(7, 10)

Ultimately, we anticipate that these data will be useful in understanding the potential cycle and interrelationship between IBD and mental health in children and young adults.

Objectives: Stream 1 – Incidence of mental health conditions

Primary Objectives

- Compare the risk and cumulative incidence of mental health conditions in children and young adults with IBD compared to matched population controls in the primary care setting, stratified by IBD type

Secondary Objectives

- Determine severity of mental health conditions in those with and without IBD (e.g. evidence of self-harm, suicide attempt, behavioural disorders)

Objectives: Stream 2 – Impacts of mental health conditions

Primary Objective:

- Determine the association of mental health conditions in children and young adults with IBD on quality-of-life indicators

Secondary Objectives:

- Compare IBD severity/disease markers in children and young adults with IBD with and without mental health illness

- Compare healthcare resource utilisation in children and young adults with IBD with and without mental health illness

Methods

The study protocol was specified a priori and registered with ClinicalTrials.gov (Study identifier: NCT05206734).

Data source

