Cox proportional hazards models will be used to compare disease incidence in PIBD cases and controls and also when comparing the associations of baseline features and outcomes within the PIBD cohort. The study start date will be the date of diagnosis of PIBD or, for controls, the date of diagnosis of their matched counterpart. The end of follow-up will be the first of; the point of data extraction (**exact date TBC**), the patient's 25th birthday, date of loss to follow-up (either GP practice deregistration or death). All individuals contributing at least six months of follow-up time in the analysis will be included. Those with existing evidence of the mental health condition prior to baseline will be excluded for analysis of that particular outcome where it would not reoccur, for example if individual has already received a diagnosis of recurrent depressive disorder they would not receive this diagnosis again, although conditions at baseline that can reoccur, such as suicide attempt, would not be excluded. Models will be adjusted for age, gender, socioeconomic status, ethnicity, and other childhood conditions (asthma, atopic dermatitis, allergic rhinitis, thyroid disease, epilepsy, diabetes, cancer, juvenile idiopathic arthritis (JIA) including systemic JIA, systemic lupus erythematosus (lupus), ankylosing spondylitis (AS) and psoriatic arthritis). Statistical significance for analyses will be reported using P values and 95% confidence intervals as appropriate.

Cumulative risk (i.e. prevalence) of the 'any psychological condition' composite outcome will be evaluated up to age 25. Cumulative incidence will be calculated by using methods to estimate risk similar to those recently published when assessing lifetime risk of other chronic conditions in the Lancet.(11, 12) Key outputs will be cumulative risk plots, presenting the cumulative incidence of the outcome by age for PIBD patients compared to controls. At a particular age, the cumulative incidence estimate can be interpreted as the lifetime incidence of the outcome up until the year of age in question. Childhood cumulative risk will be defined as the cumulative incidence at age 18.

Stream 1: Sensitivity analysis

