To evaluate the magnitude of potential bias from including, as matched controls, people who are registered with GP practices but who do not attend their practice, we also repeated the primary analysis including only controls with a least one primary care consultation in the year preceding their index date.

All statistical analyses were performed using R statistical package software version 3.4.1. The study was conducted in line with the RECORD (Reporting of studies conducted using observational routinely collected data) guidelines.(13)

Stream 2:

Stream 2: Study design

The proposed study will use the retrospectively collected data of all eligible patients within the database at the date of data extraction. Within this primary care cohort, all patients with IBD will be identified using diagnostic codes and prescription records. A diagnostic algorithm will be developed to facilitate robust case identification of IBD and IBD subtypes as well as mental health outcomes.

Stream 2: Study cohort

The eligible IBD cases will comprise all prevalent cases of IBD aged under 25 at 01/01/2015 (index date) comprising of the three main subtypes; ulcerative colitis (UC), Crohn's disease (CD) and IBD unclassified (IBDU), excluding microscopic colitis, radiation induced enterocolitis and drug-induced enterocolitis. We will extract sociodemographic details for all individuals. Sociodemographic data will comprise by age group, age at diagnosis, sex, ethnicity, and socioeconomic status. Ethnicity will be categorised as follows to be consistent with the UK official census categories: White, Asian, Black African/Caribbean, Mixed, and Other. The index of multiple deprivation (IMD) will be used as a measure of socioeconomic status. This is derived from patient postcode at the point of data extraction.

We will identify comorbid psychological condition groups in all people with PIBD. These will comprise 3 composite phenotypes; anxiety/panic disorders, major depression or depressive episodes, and other psychological conditions. Other psychological conditions will be a composite of; eating disorders, body image disorder, attention-deficit disorder (ADHD), behavioural disorders, adjustment disorder, acute stress disorder, schizophrenia, bipolar disorder and post-traumatic stress disorder (PTSD). Where numbers are sufficient, subgroups of the broad 'other psychological conditions' composite may be examined.

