At the index date, we will define groups in the IBD case population based on mental health phenotype, including a comparator group without mental health comorbidity at the index date, and compare the sociodemographic characteristics of these groups.

Stream 2: Follow-up

We will then describe incidence of each study outcome in the five years after the index date for each group, and the relative incidence of each outcome in those with and without mental health comorbidity.

Stream 2: Study outcomes

These will comprise the following.

Quality of life indicators:

Affective symptoms (depression, low mood, deliberate self-harm, suicidal ideation or parasuicide), IBD symptoms, absence from school, absence from work, unemployment, substance abuse, and sleep problems. IBD symptoms will comprise; abdominal pain, discomforts or bloating, diarrhoea, weight loss, growth retardation and tiredness/fatigue. (See Appendix 1 – Table s1 for Read Codes and SNOMED codes).

IBD severity indicators:

Medication use, surgical intervention, nutritional supplement use, and markers of nutritional status. Surgical intervention will comprise any abdominal surgery, and stoma formation (as a separate outcome). Medication use will comprise use of: rectal 5-aminosalicylic acid (5-ASA), oral 5-ASA, rectal steroids, oral steroids, antimetabolites, tumour necrosis factor inhibitors (TNFi) and other biologic therapies. The latter of these groups may not be well captured in primary care and if so this will be reported in the limitations section of the final study manuscript. Nutritional supplements will comprise the five most prescribed nutritional supplements: Modulen, Fortisip, Ensure, Osmolite, and Neocate. Nutritional markers will comprise; being underweight (under the 5th centile of weight for height or BMI < 18.5 kg/m² after age 18) and growth retardation related codes. (See Appendix 1 – Table s2 for Read Codes and SNOMED codes).

Healthcare resource utilisation:

Primary care attendances and hospital admissions. Hospital admissions will be separated into general admissions (including those for IBD) and psychiatric admissions. (See Appendix 1 – Table s2 for Read Codes and SNOMED codes).

Stream 2: Statistical methods

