We will use standard descriptive statistics (mean, standard deviations, etc) to describe the characteristics of the study cohort overall and by mental health phenotype. Across mental health condition phenotypes we will describe the incidence of recording of all the quality-of-life indicators, IBD severity markers, and healthcare resource utilisation outcomes up to five years after the index date (01/01/2015), compared to incidence in the group without mental health conditions. The end of follow-up will be the first of; 01/01/2020 (5 years after the index date) we will not follow patients up into 2020/21 due to changes in patient health behaviour and primary care interactions due to COVID-19, the patient's 25th birthday, date of loss to follow-up (either deregistration or death). All individuals contributing at least six months of follow-up time in the analysis will be included. We will not follow patients up into 2020/21 due to changes in patient health behaviour and primary care interactions due to COVID-19.

Relative incidence between those with and without mental health conditions will be estimated for repeated events (e.g. number of hospital admissions) and binary events (e.g. quality of life indicators) using, as appropriate, Poisson regression, negative binomial regression (if we need to account for overdispersion), or zero-inflated Poisson regression (if we need to model rare events). To account for variable duration of follow-up, we will include the natural logarithm of person-years of follow-up as a model offset. Confidence intervals will be estimated using robust SEs. Models will be adjusted for age, gender, socioeconomic status, ethnicity, and other childhood conditions (asthma, atopic dermatitis, allergic rhinitis, thyroid disease, epilepsy, diabetes, cancer, juvenile idiopathic arthritis (JIA) including systemic JIA, systemic lupus erythematosus (lupus), ankylosing spondylitis (AS) and psoriatic arthritis). Statistical significance for analyses will be reported using P values and 95% confidence intervals as appropriate.

Where numbers allow, we will report absolute and relative incidence in subgroups by, mental health condition group, age group (5-<12; 12-<16; 16-<18; 18-<25) (child, adolescent, young adult), and sex.

References

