Read CTV3 Code	Term ID	Description
SNOMED Code	Term ID	Description

sTable 2.2 Algorithms used to identify anxiety episodes, depression episodes, and recurrent major depression. Expressions in capitals equate to Boolean expressions. *More than 1 year ago. SSRIs = selective serotonin reuptake inhibitors, TCA = tricyclic antidepressants, MAOI = monoamine oxidase inhibitors, CBT = cognitive behavioural therapy.

Clinical entity	Definition
Anxiety	Any coded anxiety episode AND concurrent treatment for anxiety
Depressive episode	Any coded depressive episode AND concurrent treatment for depression
Recurrent depressive disorder	(Any historical code* for a depressive episode AND current treatment for depression) OR Any code for recurrent depressive disorder
Anxiety treatments	SSRIs, anxiolytics, counselling, CBT, and psychotherapy
Depression treatments	SSRIs, TCAs, MAOIs, counselling, CBT, and psychotherapy

sTable 2.3 WHO International Statistical Classification of Diseases (ICD-10) for mental health conditions

Clinical entity	ICD 10 code	Definition
Depressive episode	F32	Any coded depressive episode AND concurrent treatment for depression
Recurrent depressive disorder	F33	(Any historical code* for a depressive episode AND current treatment for depression) OR Any code for recurrent depressive disorder
Depression treatments	NA	SSRIs, TCAs, MAOIs, counselling, CBT, and psychotherapy
Anxiety	F41	Any coded anxiety episode AND concurrent treatment for anxiety
Anxiety treatments	NA	SSRIs, anxiolytics, counselling, CBT, and psychotherapy
Self-harm	X60-X84	Any diagnostic or indicative code for any form of self-harm, including suicide attempt
Eating disorders	F50	Any diagnostic or indicative code for eating disorders

Body image disorders	F45.2	Any diagnostic or indicative code for body image / dysmorphic disorder (excluding hypochondriacal disorders not associated with body image)
Attention-deficit disorders	F90.0	Any diagnostic or indicative code for disturbance of activity and attention
Behavioural disorders	F91 F92	Any diagnostic or indicative code for conduct disorders
Adjustment disorders	F43.2	Any diagnostic or indicative code for adjustment disorders
Acute stress disorders	F43.0	Any diagnostic or indicative code for acute stress disorders
Post-traumatic stress disorder	F43.1	Any diagnostic or indicative code for Post-traumatic stress disorder

Appendix 3

sTable 3.1 Read and SNOMED codes to be used to identify quality of life

Depressive episode		

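### Stream 2's affective-symptoms indicator counts depression with almost the same codes that define the depression phenotype, and no rule separates re-recording from recurrence or onset

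*Combined protocol and SAP*

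**What the plan says.** The Stream 2 primary objective is to "Determine the association of mental health conditions in children and young adults with IBD on quality-of-life indicators". Under Stream 2: Study cohort the exposure groups are set out: "These will comprise 3 composite phenotypes; anxiety/panic disorders, major depression or depressive episodes, and other psychological conditions". Groups are fixed at the index date, 01/01/2015, "including a comparator group without mental health comorbidity at the index date".

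Under Stream 2: Study outcomes, the first of seven quality-of-life indicators is "Affective symptoms (depression, low mood, deliberate self-harm, suicidal ideation or parasuicide". Stream 2: Statistical methods describes the "incidence of recording of all the quality-of-life indicators" for up to five years, and gives these indicators as an example of an outcome type: "binary events (e.g. quality of life indicators".

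The code list titled "Read and SNOMED codes to be used to identify quality of life" is sTable 3.1 in Appendix 3. Study outcomes cites Appendix 1, Table s1 instead, so the link rests on the table's title. sTable 3.1 opens with a depressive-episode block, followed by blocks for recurrent depressive disorder, depressive symptoms and parasuicide.

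The only prior-condition rule is in Stream 1, which excludes people for "that particular outcome where it would not reoccur, for example if individual has already received a diagnosis of recurrent depressive disorder". Stream 2 does not repeat it. Stream 2: Study design promises a diagnostic algorithm that will cover mental health outcomes. The algorithms actually given, in sTable 2.2, are not tied to Stream 2 outcomes.

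**The concern.** A person enters the depression phenotype because depression is already on the record. The plan then counts whether depression is recorded again, and compares that with people chosen for having no such condition at index. A general practice record can carry the same problem forward through reviews, treatment entries, remission entries and history entries. None of these need mark anything new.

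At stake is one relative incidence under the Stream 2 primary objective. If it came out well above 1, a reader would take it to mean that people with IBD and depression go on to have worse quality of life. Part of the ratio would only show that recorded depression tends to be recorded again, and the planned analysis could not say how large that part is.

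**Working it through.** **1. Code overlap.** The plan states no figure for this, so there is none to reproduce. The depressive-episode block of sTable 2.1 (phenotype) was compared with that of sTable 3.1 (outcome), within each coding system.

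| System | sTable 2.1 | sTable 3.1 | Shared |
|---|---|---|---|
| Read V2 | 50 | 50 | 50 |
| CTV3 | 58 | 58 | 55 |
| SNOMED | 141 | 139 | 139 |
| Total | 249 | 247 | 244 |

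244/249 = 98.0%. Three of the five mismatches are CTV3 codes with identical descriptions and near-identical spelling (XSGom/XGom, XSGon/XGon, XaCIu/XaClu). A fourth, antenatal depression, appears in sTable 3.1 beside another code. Matched by code or description, the overlap is 248/249 = 99.6%.

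**2. Outcome entries that need not mark a new event** (depressive-episode and recurrent-disorder blocks of sTable 3.1; terms for psychosis in remission not counted).
- History, or full/unqualified remission: Read V2 E1126, E1136, Eu334; CTV3 E1126, E1136; SNOMED 19527009, 161469008, 764701000000109, 764711000000106, 16265061000119100, 68019004. 3 + 2 + 6 = 11.
- Partial or unspecified remission, which can mean continuing symptoms: Read V2 E1125, E1135; CTV3 E1125, E1135; SNOMED 30605009, 33135002, 70747007, 764691000000109, 16265301000119100. 2 + 2 + 5 = 9.
- Care or treatment, counted by description: counselling for depression, counselling for postnatal depression, care management, two self-help referrals, and full-dose long-term treatment. 6.

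**3. Would sTable 2.2 close the gap?** If it does not govern the outcome, any listed code counts. If it does, a depressive episode needs a code with concurrent treatment, which a re-recorded code in someone still treated satisfies. The recurrent-disorder rule also accepts a code more than one year old plus current treatment. A pre-index code with continuing treatment therefore qualifies in follow-up without any new depression code.

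**4. Other phenotypes.** Eleven outcome codes also sit in the anxiety block: E2003 and Eu412 (Read V2), X00Sb (CTV3), and eight SNOMED mixed or co-occurrent terms. Three sit in the adjustment-disorder block: E291. (Read V2), 192046006 and 192049004 (SNOMED). Three is a lower bound for the 'other' phenotype, because several of its lists, including schizophrenia and bipolar disorder, are blank.

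**5. Illustration, on assumed inputs only.** The documents give no re-recording rate. Suppose the true five-year risk of new depression is r in both groups (true ratio 1.0), follow-up is equal, and old depression is independently re-recorded in a share q of the depression group and in nobody in the comparator. The apparent ratio is [1 − (1 − r)(1 − q)]/r.

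| r | q = 10% | q = 30% | q = 50% |
|---|---|---|---|
| 5% | 2.9 | 6.7 | 10.5 |
| 10% | 1.9 | 3.7 | 5.5 |
| 20% | 1.4 | 2.2 | 3.0 |

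For example, r = 10% and q = 10% give 1 − 0.90 × 0.90 = 0.19, and 0.19/0.10 = 1.9. At r = 10%, pooling with other affective events at 10% in both groups softens this: 0.271/0.19 = 1.43 for q = 10%, and 0.595/0.19 = 3.13 for q = 50%. Any re-recording in the comparator lowers it too: at 5% there, the unpooled figures become 0.19/0.145 = 1.31 and 0.55/0.145 = 3.79. These are cumulative risk ratios. The plan uses count models with a person-years offset and stops follow-up at the 25th birthday, so they show the mechanism and not an expected result.

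**The case against.** The best defence is that the plan promises association and incidence of recording, not onset. Depression that continues through follow-up is a real burden on quality of life, so counting it is not an error. That stands in part: persistence is worth reporting. It should be labelled as persistence, because set against a comparator selected for having no condition at index, the ratio combines different kinds of event in the two groups. It also does not rescue the history and full-remission entries, which describe no current burden.

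A second defence is that the event definition is still to come, since a diagnostic algorithm is promised and many code lists are blank. That is fair as to the state of the document. But the depression lists are filled in, and the algorithms supplied in sTable 2.2 would not separate old from new.

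Third, the reach is limited to one of seven indicators, and mainly to one component of it. The plan does not rule out reporting the components separately, which would confine the problem to depression and the overlapping low-mood codes. This stands.

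A reader might infer that the overlap extends to other indicators, for instance from truancy (under absence from school) to behavioural disorders. The behavioural-disorders code list is blank, so the documents cannot show it. Nor are the history-of-attempt entries under parasuicide circular: self-harm and suicide attempt belong to no Stream 2 phenotype.

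**Conclusion.** The point holds for the depression component of the affective-symptoms indicator and for any pooled affective result that contains it. The firm parts are the 98.0% code overlap, the 26 entries (11 + 9 + 6) that need not mark a new event, and the absence of a Stream 2 rule. It follows that the relative incidence would mix re-recording, recurrence and onset.

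Inflation for the depression phenotype is probable, on the assumption that existing depression is re-recorded more often there than in a group selected to be free of it. The effect is likely smaller for the anxiety phenotype (11 shared codes) and for the 'other' phenotype (at least 3).

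A reader might go further and infer that the ratio is inflated by a known factor, or that the Stream 2 primary objective fails as a whole. The documents support neither: they give no re-recording rate, and this evidence bears on one indicator of seven. The matter should be fixed before data extraction.

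**What to change.** 1. Report depression separately from low mood, deliberate self-harm, suicidal ideation and parasuicide. Do not pool it into the quality-of-life relative incidence for the depression phenotype.
2. Report follow-up depression as onset in people with no pre-index depression code, in every group, and separately as recurrence or persistence in people with one. Recurrence should need a code-free gap fixed before extraction, with a shorter and a longer gap as sensitivity analyses.
3. Remove the 11 history and full/unqualified-remission entries from the outcome list. Do not let the 9 partial/unspecified-remission or 6 care/treatment entries start an event by themselves.
4. Remove from the low-mood list the four codes that also sit in the phenotype list, with their true equivalents in other coding systems: 394924000 with 1B1U. and XaImU; 366979004 with 1BT.. and XE0re; 272022009 with XM0CR; and X00SO alone. Keep 1B17. ('Depressed'), because X00SO is labelled as a depressive disorder in the depressive-episode blocks of both tables.
5. State whether sTable 2.2 governs Stream 2 outcomes. If it does, do not let a pre-index historical code plus current treatment define a follow-up event.

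As a separate code-list cleaning item, review the three earlier-attempt entries under parasuicide (146A., 161474000, 23233009).

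The cost is protocol wording and code-list work, with no new data. The downside is fewer affective events. Under step 4 the low-mood list loses 3 + 3 + 2 + 1 = 9 of its 32 codes (6 Read V2, 9 CTV3, 17 SNOMED) and keeps 23.

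### Stream 2 counts medication use as incident IBD severity in prevalent cases, with no rule separating new use from treatment carried over from before the index date and no adjustment for baseline treatment

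*Combined protocol and SAP*

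**What the plan says.** The first secondary objective listed for Stream 2 is to "Compare IBD severity/disease markers in children and young adults with IBD with and without mental health illness". Under 'Stream 2: Study outcomes', the severity indicators are "Medication use, surgical intervention, nutritional supplement use, and markers of nutritional status", and medication use means use of "rectal 5-aminosalicylic acid (5-ASA), oral 5-ASA, rectal steroids, oral steroids, antimetabolites, tumour necrosis factor inhibitors (TNFi) and other biologic therapies". On biologics, the same section adds that "The latter of these groups may not be well captured in primary care". Its only remedy is a sentence in the limitations of the final manuscript.

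'Stream 2: Study cohort' defines the population: "The eligible IBD cases will comprise all prevalent cases of IBD aged under 25 at 01/01/2015". 'Stream 2: Study design' finds IBD cases partly from prescription records. 'Stream 2: Follow-up' says the study will "describe incidence of each study outcome in the five years after the index date for each group", together with relative incidence by mental health status.

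'Stream 2: Statistical methods' specifies Poisson-type models with a log person-years offset, adjusted for age, sex, deprivation, ethnic group and a list of childhood comorbidities. Treatment at index, IBD subtype and time since diagnosis are not in that list. The section gives hospital admissions as an example of a repeated event and quality-of-life indicators as an example of a binary one. It does not say which form medication use takes.

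The Background cites evidence that "symptoms of anxiety and depression may decrease adherence to treatment, thus impacting on longer term disease outcomes".

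**The concern.** Incidence needs a starting state in which the event has not yet happened. For a drug class in a prevalent cohort, that state has to be defined, and Stream 2 does not define it. Stream 1 does handle the problem: people with prior evidence of a condition are excluded from the analysis of that outcome where it would not recur. Stream 2 has no counterpart for drugs.

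Three consequences follow.

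- A patient on maintenance treatment at index can register an event at the next repeat prescription. That records continuation, not worsening.
- If the groups differ in treatment at index, the ratio carries that difference forward, because the models do not include it. The Background itself associates depression with active disease and current steroid use.
- If anxiety or depression reduces adherence, as the Background says may happen, a ratio below 1 for a maintenance drug could mean milder disease or poorer adherence. The planned analysis cannot tell these apart.

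At stake is whether the medication results can inform the severity objective.

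**Working it through.** The documents give no sample size, drug-use rate, adherence figure or capture rate for Stream 2, so there is no planned figure to reproduce. All inputs below are assumptions that show the mechanism.

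**1. Carry-over, any-record outcome, equal follow-up.** Let p be the share on the drug at index in both groups, all of whom have a later prescription. Let the new-start risk in the rest be 10% without and 20% with mental illness (true ratio 2.0). Recorded risk = p + (1 − p) × new-start risk.

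| p | Without | With | Recorded ratio |
|---|---|---|---|
| 0.30 | 0.30 + 0.70 × 0.10 = 0.37 | 0.30 + 0.70 × 0.20 = 0.44 | 1.19 |
| 0.50 | 0.50 + 0.50 × 0.10 = 0.55 | 0.50 + 0.50 × 0.20 = 0.60 | 1.09 |
| 0.70 | 0.70 + 0.30 × 0.10 = 0.73 | 0.70 + 0.30 × 0.20 = 0.76 | 1.04 |

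**2. Difference at index, no new-start effect.** Take a new-start risk of 10% in both groups and 70% of the comparator on the drug at index (recorded risk 0.73). If 80% of the mental-illness group are on it, their risk is 0.80 + 0.20 × 0.10 = 0.82 and the ratio is 0.82/0.73 = 1.12. If 60% are on it, 0.60 + 0.40 × 0.10 = 0.64 and the ratio is 0.64/0.73 = 0.88. Neither departure from 1 reflects anything after index.

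**3. Unequal follow-up.** If 95% of both groups have any record, mean follow-up of 2.5 versus 3.5 years alone gives (0.95/2.5)/(0.95/3.5) = 1.40 before age adjustment. Follow-up can differ because it ends at the 25th birthday.

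**4. Adherence, prescription counts.** Recorded ratio = true ratio × adherence ratio, which falls below 1 when the adherence ratio is below 1/(true ratio): 0.80 for a true ratio of 1.25, 0.67 for 1.5.

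- True ratio 1.25, adherence ratio 0.7: 1.25 × 0.7 = 0.88, reversed.
- True ratio 1.5, adherence ratio 0.8: 1.5 × 0.8 = 1.20, attenuated only.
- Steroids, if poor adherence also raises flares by a factor of 1.5: 1.25 × 1.5 × 0.7 = 1.31, inflated.

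**5. Under-capture of biologics.** With true use of 20% versus 15% and capture s equal in both groups, (0.20 × s)/(0.15 × s) = 1.33 for any s. Reversal needs capture in the mental-illness group below 0.15/0.20 = 0.75 of that in the comparator.

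**The case against.** The plan has a fair defence. It never says that a repeat prescription after index is an incident event, nor that lower use will be read as milder disease. It reports each outcome separately, with no severity composite. Surgery, stoma formation, underweight and growth codes do not depend directly on whether a drug is prescribed. The capture problem is disclosed.

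The adherence argument also has limits. For an any-record outcome over five years, one prescription is enough, so partial non-adherence barely moves the result. It matters mainly for prescription counts. That cohort members are already treated is inferred from prevalent status and prescription-based case finding; it is not stated.

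A reader might go further and infer that the severity objective as a whole will come out in the wrong direction. The documents do not support that. The adherence statement is hedged, equal under-capture leaves a ratio unchanged, steroid use may rise, and the non-drug markers stand apart.

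Restricting to new users has its own difficulty. If depression goes with active disease and steroid use, excluding prior users removes more of the depression group.

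These points limit the concern but do not answer it. Silence on what counts as use leaves carry-over open, and a limitations sentence about biologics covers neither carry-over nor baseline treatment.

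**Conclusion.** The concern holds for the medication indicators only. The plan has no rule separating new from continuing use in a prevalent cohort and no adjustment for baseline treatment, IBD subtype or disease duration. As written, a drug-class ratio near 1 may be carry-over, and one away from 1 may reflect the position at index. A ratio below 1 for a maintenance drug is ambiguous as a severity signal.

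The loss of signal can be large: a new-start ratio of 2.0 shows as 1.04 to 1.19 when 70% to 30% of both groups are on the drug at index. Those figures are assumed and apply to an any-record outcome with equal follow-up. The documents do not settle the direction of the net bias. This is a worthwhile, inexpensive improvement to an outcome definition. It does not show that the severity objective fails.

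**What to change.** In 'Stream 2: Study outcomes' and 'Stream 2: Statistical methods':

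1. For the severity comparison, define a medication event as the first recorded start of that class after index in patients with no earlier record of it. For oral steroids, use a new course after a prespecified prescription-free look-back, for example 12 months, varied in sensitivity analysis.
2. Adjust for, or stratify by, pre-index treatment, IBD subtype and time since diagnosis. Age at diagnosis is already to be extracted. This step is needed as well as the first, because exclusions for prior use may fall unequally. Report the number excluded in each group.
3. Report any-use results for maintenance drugs alongside, labelled as treatment use or persistence.
4. Draw no severity conclusion from biologic records if capture proves poor.
5. State whether each medication outcome is binary or a count.

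The work is outcome wording plus a look back through prescriptions in the same records. The cost is fewer events per class, and each new-start result applies only to patients not already on that class. Adjusted ratios will describe change after index, not the whole difference between the groups.
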